6.3. Expected number of subjects and justification

A total of 120 volunteers diagnosed with any type of cancer, in stages I-III, who are about to start or have received a maximum of 1 dose of chemotherapy treatment will be studied.

Two study populations are contemplated: (i) population that will receive the PB-011 cream; (ii) population that will receive the PB-012 cream. Both populations will apply the cream on their hands once a day. If sensory discomfort or, in the worst case, peripheral neuropathy appear during the chemotherapy treatment period, the application will be increased to twice daily on the affected areas (generally hands and feet).

The number of volunteers for the study is 60 for each population. This value is based on: (i) a difference of 2 points between both populations (PB-011 and PB-012), on a satisfaction scale of

0 to 10 points, with 0 being very dissatisfied and 10 very satisfied, or 2 points on the Von Frey scale; (ii) a variability (standard deviation) of 3 points in each population; (iii) a p-value of statistical significance <0.05 and, (iv) a probability of finding a statistically significant difference for the p-value <0.05 of 95%.

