6. SELECTION OF SUBJECTS

The inclusion of 120 patients who have been diagnosed with cancer in stages I-III and who are going to start chemotherapy treatment is proposed. Once the treatment is finished, the degree of cutaneous comfort will be compared between the patients who have developed peripheral neuropathy in both groups.

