7.2. Study development

When a subject meets all the inclusion criteria and none of the exclusion criteria and has signed the informed consent document, he/she is electable to enter the study. The researchers will collect the data of each volunteer and notify Prospera Biotech of their inclusion. Patients will

receive the cream when they start the chemotherapy treatment. Creams will be either sent directly to the participants' home or sent in advance to the centers and stored there at room temperature (15-25°C) until distributed to participants. The principal investigator will create the Data Notebook for each subject, anonymizing the personal and clinical data in all cases. The type of product to be assigned will be determined by the randomization procedure.

Subjects taking part in the study should apply a sufficient amount of cream to their hands once a day for the duration of their chemotherapy treatment. Those subjects who develop skin sensitivity or peripheral neuropathy should undergo the following procedures:

1. Increase the frequency of use of the cream to twice a day in all affected areas.
2. Once the chemotherapy treatment is finished: evaluation of the degree of skin satisfaction by means of a questionnaire that assesses the Dermatology Life Quality Index [DLQI] (Annex II) and the degree of satisfaction with the cream (Annex IV). Evaluation of the discomfort generated by peripheral neuropathy through a follow-up questionnaire (Annex III). Measurement of skin sensitivity using Von Frey hairs for patients who voluntarily wish to do so. These procedures will be carried out by the study collaborators of each center. In case of need, Prospera Biotech team could also contribute to make the follow-up (questionnaires) telematically.

The study procedures are included in section 8.2.

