8. STUDY DEVELOPMENT AND EVALUATION OF THE RESPONSE

8.1. Study variables

Main Variable: degree of skin satisfaction/comfort with the skin in the palmar and plantar regions, evaluated by means of the DLQI questionnaire.

Secondary Variables:

- Skin sensitivity quantifiable by the Von Frey filament test for patients who voluntarily so wish.
- Follow-up of discomfort skin sensations experienced by patients, evaluated by means of a brief questionnaire.

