8.2. Collection of variables

The main variable, degree of skin satisfaction/comfort, will be evaluated using the DLQI^{12, 13} questionnaire available in ANNEX II.

Mechanical sensitivity will be assessed by means of the Von Frey filament test in patients who voluntarily want to undergo it. The pain threshold and mechanical allodynia of patients with post-chemotherapy polyneuropathy will be measured before starting the study and once the chemotherapy treatment is over, expressing the threshold in the minimum number of pressure units that trigger pain in patients with the corresponding filament. of Von Frey approved.

The follow-up of the patients will be carried out through the usual oncological control during treatment. If the patients develop sensory or skin discomfort during this period, at the end of the treatment a check-up will be carried out using the following questionnaires:

- Follow-up of discomfort sensations available in a questionnaire derived from the Leonard Scale (ANNEX III).
- Degree of skin satisfaction by means of the Dermatology Life Quality Index [DLQI] (Annex II).
- Degree of satisfaction with the cream (Annex IV).

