12. STATISTICAL ANALYSES

The analysis of the results of this study will be approached from two perspectives. On the one hand, the modified intention-to-treat (MITT) population will be analyzed, which corresponds to all those subjects who have used the product at least once and for whom satisfaction data is available. On the other hand, a per-protocol analysis will be carried out in which all randomized subjects who have followed the study instructions until the end of the study will be included.

The clinical evaluation data may be analyzed as quantitative or qualitative variables. In the first case, the results will be expressed as mean \pm standard deviation, minimum and maximum. In the case of qualitative variables, the results will be expressed as frequency and percentage. For all the parameters to be measured (both clinical variables and responses to questionnaires) there will be a baseline measurement taken before the start of the protocol that will serve as a control measurement. The change in the main variable (degree of satisfaction) will be analyzed

using the paired Student's T test. The change in the secondary variables will be studied according to their nature (qualitative or quantitative variables) and applying the corresponding test in each case: Chi square, Student's T, ANOVA, Kruskal-Wallis or Mann-Whitney U. The impact of each variable on the main variable will be assessed, especially the impact of treatment, diagnosis, age and gender.

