ANNEX IV: SATISFACTION QUESTIONNAIRE

Title: Study for the evaluation of the degree of skin satisfaction of cosmetic creams PB-011 and PB-012 for sensitive skin in oncological patients affected by a palmoplantar polyneuropathy secondary to taxanes.

Principal Investigator: [name]

Reference: 20PB-02

1. Has applying the cream to your hands and/or feet caused you any discomfort?

Nothin									Many
1	2	3	4	5	6	7	8	9	10

2. Has the application of the cream to your hands and/or feet generated any kind of skin reaction?

Nothin									Many
1	2	3	4	5	6	7	8	9	10

3. How would you define your degree of satisfaction with the cream?

Nada									Mucho
1	2	3	4	5	6	7	8	9	10

If, sensorial discomfort or CIPN have appeared during the chemotherapy treatment please answer also:

1. When you apply the cream to your hands and/or feet, do you feel any relief from any of the sensations that bother you?

YES	NO
-----	----

2. Has the application of the cream generated comfort in your skin sensitivity on the hands

and/or feet?

Nothing										A lot
1	2	3	4	5	6	7	8	9	10	

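### The 95% power in section 6.3 was worked out for a different score, patient group and test from those of the planned main analysis

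*Combined protocol and SAP*

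**What the plan says.** - **Sample size (section 6.3).** 60 per arm, from a 2-point difference between PB-011 and PB-012, SD 3 in each arm, significance at 0.05 and 95% power. The scale is "0 to 10 points, with 0 being very dissatisfied and 10 very satisfied, or 2 points on the Von Frey scale". Sections 1 and 3 repeat the 60 as a number that secures statistical significance.
- **Main variable (section 8.1).** "Main Variable: degree of skin satisfaction/comfort with the skin in the palmar and plantar regions, evaluated by means of the DLQI questionnaire". Von Frey testing is a secondary variable for volunteers only, and section 8.2 describes it as "expressing the threshold in the minimum number of pressure units that trigger pain in patients with the corresponding filament".
- **Who is compared.** Section 6: "the degree of cutaneous comfort will be compared between the patients who have developed peripheral neuropathy in both groups". Section 7.2, introducing the end-of-treatment questionnaires: "Those subjects who develop skin sensitivity or peripheral neuropathy should undergo the following procedures". Section 8.2: "If the patients develop sensory or skin discomfort during this period, at the end of the treatment a check-up will be carried out". Section 12 defines the modified intention-to-treat set as users of the product who have satisfaction data, and a per-protocol set as randomised patients who followed instructions to the end.
- **Test (section 12).** Change in the main variable is analysed "using the paired Student's T test". A later sentence says that the effect of treatment and of other factors on the main variable will be assessed, but names no test or model.
- **Aims.** Sections 1 and 4 state a hypothesis that care with the creams improves satisfaction and comfort. Section 4 also says the study is meant to establish which cream satisfies patients more.
- **Timing.** Section 3 has satisfaction assessed fortnightly when there is discomfort. Sections 7.2 and 8.2 place the DLQI at the end of chemotherapy. Section 12 promises a baseline for every parameter.

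**The concern.** A power figure belongs to one outcome, one set of patients and one test. The figure in section 6.3 differs from the planned main analysis on all three. It is also the only justification given for 120 patients, so a reader would credit the main comparison with 95% power that the documents do not establish.

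The test matters most. A paired t test asks whether scores changed within patients. It does not ask whether one cream did better than the other, which is the comparison section 6.3 powers and section 4 sets as an aim. As written, that question has no named test. With score, analysed group, time point and contrast all unsettled, each could be chosen once the data are in hand.

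**Working it through.** **Step 1: reproduce the plan's figure.** Inputs from section 6.3: difference 2, SD 3, alpha 0.05, power 95%. Sidedness is not stated; I take two-sided. Equal arms are assumed.

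Normal approximation: n per arm = 2 × SD² × (z₀.₉₇₅ + z₀.₉₅)² / difference² = 2 × 9 × (1.960 + 1.645)² / 4 = 58.5, so 59. The exact t calculation gives 59.5, so 60. Power of the two-sample t test at 60 per arm is 95.2%. The one-sided version gives 49 per arm and does not match. Section 6.3 is therefore a two-sided, two-sample comparison of means, computed correctly.

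**Step 2: look for an allowance.** The requirement is 59.5 and the enrolment is 60. Nothing is left for patients who are enrolled but not analysed. The plan does not say in words that all 60 are counted; this follows from the absence of any inflation.

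**Step 3: set the calculation beside the analysis.**

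| | Section 6.3 | Planned main analysis |
|---|---|---|
| Score | 0–10 satisfaction, or Von Frey points | DLQI (8.1, 8.2) |
| Difference and SD | 2 and 3 | none given for the DLQI |
| Patients | all 60 per arm | neuropathy (6); skin sensitivity or neuropathy (7.2); sensory or skin discomfort (8.2); satisfaction data available (12) |
| Contrast | between creams | within patient, paired t (12) |

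The nearest instrument to a 0–10 satisfaction scale is the Annex IV item on satisfaction with the cream. It runs from 1 to 10, rates the cream rather than the skin, and is not listed in section 8.1. The Von Frey alternative cannot share the same 2 points and SD 3, because it is a threshold in pressure units.

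**Step 4: what fewer analysed patients would do, on section 6.3's own inputs.** The standardised difference is 2/3 = 0.667, tested by two-sample t, two-sided 0.05. Section 3 gives neuropathy rates of up to 95% (the platinum agent it names) and up to 80% (taxanes). I use them as an assumed analysed share, equal in both arms. The 50% row is purely an assumption.

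| Share analysed | n per arm | Power |
|---|---|---|
| 100% | 60 | 95.2% |
| 95% | 60 × 0.95 = 57 | 94.2% |
| 80% | 60 × 0.80 = 48 | 89.8% |
| 50% | 60 × 0.50 = 30 | 71.9% |

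These rows describe the 0–10 scale, not the DLQI.

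**Step 5: what can be said for any score.** With no DLQI SD, only the detectable difference in SD units can be given. For 95% power it is 0.66 SD at 60 per arm and 0.74 SD at 48. The SD must be that of the quantity actually compared.

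**The case against.** **The arithmetic is correct and the study is called a pilot.** Both are true. But a pilot label does not support a 95% power claim, and sections 1 and 3 present the number as confirmatory.

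**The paired test has a purpose.** This stands. Sections 1 and 4 state an improvement hypothesis, and a paired test suits it. A reader might infer that the test is simply wrong and should go. The documents do not support that: they state two aims and name a test for only one. Nor does any passage plan to judge the creams by setting one arm's paired p-value against the other's, so errors from that practice are not charged to the plan.

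**Section 12 does mention the effect of treatment on the main variable.** It does, but without a test or model. The between-group tests it lists are assigned to secondary variables.

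**Most patients may become symptomatic, so little is lost.** This partly stands. At the section 3 rates the loss is modest, to 94% or 90%. Those rates are maxima for neuropathy, and the symptomatic group in sections 7.2 and 8.2 is wider, so the true share is unknown in either direction.

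**Annex IV appears to put its first three questions to everyone.** Its second part opens with "If, sensorial discomfort or CIPN have appeared during the chemotherapy treatment please answer also", from which a reader might infer a contradiction with sections 7.2 and 8.2. The documents support only an ambiguity. Annex IV does not say who receives the form, and a patient with skin discomfort alone could receive it under section 8.2 and skip the second part.

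**Conclusion.** The concern holds and should be corrected before analysis. The 95% in section 6.3 is right for its own inputs but is not the power of the planned main analysis, which differs in score, patients and test. The score mismatch and the missing between-cream test are plain on the page. The population point rests on reading 60 per arm as full enrolment without allowance. Its size (94%, 90% or 72% with 57, 48 or 30 analysed per arm) rests on assumed shares and on the 2-point difference and SD 3 of a scale that is not the main variable.

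A reader might conclude that the trial is underpowered. The documents do not show that. Without a DLQI difference or SD, power on the DLQI is unknown and could be adequate or poor. What is shown is that the stated justification does not apply to the planned analysis.

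**What to change.** 1. Name one primary score and use it in sections 6.3, 8.1 and 12. The documents do not settle which was meant, so the sponsor must choose.
   - *If the DLQI is kept:* schedule its baseline in sections 7.2 and 8.2, to match section 12. Section 8.2 at present places only Von Frey before the study.
   - *If an Annex IV item is chosen:* make the DLQI secondary, reconcile the 1–10 and 0–10 ranges, and state who completes the form. Compare end scores only, and exempt the item from section 12's baseline statement, since satisfaction with a cream has no value before use.
2. State a between-cream primary comparison in section 12, for example end-of-treatment DLQI adjusted for baseline DLQI. Keep the paired test for the within-cream hypothesis.
3. State one analysed group and reconcile sections 6, 7.2 and 8.2 with the modified intention-to-treat and per-protocol definitions. If the group is limited to symptomatic or neuropathy patients, say that it is formed after randomisation, so the comparison loses that protection if a cream affects incidence. Report incidence by arm.
4. Reconcile the time point: fortnightly in section 3, end of treatment in sections 7.2 and 8.2.
5. Restate section 6.3 for that score, test and expected analysed number. Drop the 95% unless it holds. Otherwise give the detectable difference for 95% power (0.66 SD at 60 per arm, 0.74 SD at 48) and call it a pilot size.
6. Delete the Von Frey alternative from section 6.3, and amend the statement in sections 1 and 3 that the size secures significance.

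**Cost.** Mostly rewording and one recalculation. A baseline DLQI, or a short end form for symptom-free patients if they are to be analysed, may need scheduling. The stated power may become less favourable. No extra patients are needed if the power figure is restated rather than held at 95%.

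### Section 6.3 claims 95% power for a Von Frey difference as well, but that test is voluntary, its final measurement is listed only for symptomatic patients, and its SD is unsupported

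*Combined protocol and SAP*

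**What the plan says.** The sample-size paragraph is in section 6.3: "The number of volunteers for the study is 60 for each population". Its first input is "a difference of 2 points between both populations (PB-011 and PB-012") on a 0 to 10 satisfaction scale, and the same item continues "or 2 points on the Von Frey scale". The remaining inputs are given once and so serve both outcomes: "a variability (standard deviation) of 3 points in each population", "a p-value of statistical significance <0.05", and a 95% chance of reaching significance.

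Three other sections limit who takes the Von Frey test:

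- Section 8.1 lists it among the secondary variables: "Skin sensitivity quantifiable by the Von Frey filament test for patients who voluntarily so wish".
- Section 8.2: "Mechanical sensitivity will be assessed by means of the Von Frey filament test in patients who voluntarily want to undergo it". This section plans one measurement before the study starts and one after chemotherapy ends, and expresses the threshold in pressure units.
- Section 7.2: "Measurement of skin sensitivity using Von Frey hairs for patients who voluntarily wish to do so". This sits in a list of procedures for subjects who develop skin sensitivity or peripheral neuropathy, under the step that follows the end of chemotherapy.

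No section gives an expected uptake, a minimum number tested, an expected symptomatic fraction for this trial, or an increase in the sample size for patients not tested. Section 12 adds that every parameter will have a baseline measurement, and leaves the test for secondary variables to be chosen by the nature of the variable.

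**The concern.** The word *or* in 6.3 gives Von Frey the same sample size and power as satisfaction. That sample size counts everyone who receives a cream, whereas a Von Frey comparison can use only those who volunteer and who also have an end-of-treatment value. Under 7.2 the second condition removes patients who stay free of symptoms.

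What is at stake is how a Von Frey result is read. A non-significant difference would be set against a stated 95% power and taken as fairly strong evidence that the creams do not differ on mechanical sensitivity. If far fewer than 60 per arm are tested, or if the SD is wrong for this measure, the result carries much less information than 6.3 implies.

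**Working it through.** **Inputs from section 6.3.** Difference δ = 2; SD σ = 3 in each arm; α = 0.05; power 95%; 60 per arm. Sidedness is not stated.

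**Step 1. Reproduce the plan's figure.** Normal approximation, two-sided:

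n per arm = 2 × (1.960 + 1.645)² × σ²/δ² = 2 × 12.995 × 9/4 = 58.5, rounded up to 59.

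The two-sample t-test gives 59.45, rounded up to 60. One-sided testing gives 49 (normal) or 50 (t-test), so 6.3 must be two-sided. At 60 per arm the t-test power is 95.2%. The plan's figure is reproduced and has almost no slack: 59.45 needed, 60 planned.

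**Step 2. Power when fewer are tested.** For n tested per arm, power comes from the noncentral t distribution with 2n − 2 degrees of freedom and noncentrality (δ/σ) × √(n/2). The normal approximation is Φ[(2/3) × √(n/2) − 1.960]. For n = 30: (2/3) × √15 = 2.582, and Φ(0.622) = 73.3%; the t-test gives 71.9%.

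The number tested per arm is 60 × symptomatic fraction × uptake. Neither fraction is in the documents as an expectation for this trial. Both are assumptions, taken as equal in the two arms.

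| Symptomatic (assumed) | Uptake (assumed) | Tested per arm | Power, normal | Power, t-test |
|---|---|---|---|---|
| 100% | 100% | 60 | 95.5% | 95.2% |
| 100% | 95% | 57 | 94.5% | 94.2% |
| 100% | 80% | 48 | 90.4% | 89.8% |
| 100% | 50% | 30 | 73.3% | 71.9% |
| 80% | 100% | 48 | 90.4% | 89.8% |
| 80% | 75% | 36 | 80.7% | 79.7% |
| 80% | 50% | 24 | 63.7% | 61.8% |

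The 80% symptomatic figure is for illustration only. Section 3 gives it as an upper figure for taxanes, and the trial admits other agents.

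**Step 3. The units.** Power depends on δ/σ, here 2/3. Section 6.3 gives 2 and 3 in points, and the SD of 3 also serves a 0 to 10 questionnaire scale. Section 8.2 records a threshold in pressure units. The documents contain no conversion between the two and no source for the Von Frey SD. The table therefore shows what follows from 6.3's own inputs; it is not an estimate of the trial's actual Von Frey power.

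**The case against.** The strongest reply is that Von Frey is only a secondary measure in a study that section 1 calls a pilot, that the arithmetic in 6.3 is right, and that uptake could be close to complete. All of this stands. At 95% uptake with everyone symptomatic the loss is about one point (95.2% to 94.2%), and neither the 60 per arm nor the satisfaction calculation is disturbed. But 6.3 itself names Von Frey as a basis for the sample size, and a claim that needs near-universal testing does not fit a test described as optional in three places.

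A second reply is that the power table rests on assumed uptake and a doubtful SD, and that section 12 leaves open whether a t-test or a rank test will be used. That also stands. It limits how precisely the shortfall can be stated, but it does not support the 95%.

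A reader might go further and infer from 7.2 that patients choose the test only after months of cream use, so that the volunteers are self-selected and the comparison biased. The documents do not support this. Section 8.2 plans a Von Frey measurement before the study starts and section 12 a baseline for all parameters, so volunteers would normally be identified before using any cream. What remains is possible loss between the baseline and final tests, and a mismatch between 7.2 and 8.2 that needs clearing up.

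A reader might also think that recording the choice at consent would restore a fully randomised comparison. It would not do so alone, because 7.2 still lists the final test only for patients who develop symptoms. The consent pages and the Data Notebook (Annex I) are not available here, so whether the choice is already recorded cannot be judged.

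**Conclusion.** The point holds as an internal inconsistency, not an arithmetic error. Section 6.3's 95% power is correct for 60 evaluable patients per arm on a scale with an SD of 3. It is not supported for Von Frey, for three separate reasons: the test is voluntary, its end-of-treatment measurement is listed only for symptomatic patients, and its SD is given in points while the result is in pressure units.

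The direction is certain under 6.3's own inputs: appreciably fewer than 60 tested per arm means less than 95% power. The size is not fixed by the documents. It runs from trivial at 95% uptake to a power of 61.8% at 24 tested per arm, with a difference of 2, an SD of 3, a two-sided t-test at 0.05 and equal numbers in the arms. The third reason applies even at full uptake.

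This does not show that the trial is too small for its satisfaction comparison, nor that the Von Frey comparison is biased.

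**What to change.** 1. In 6.3, delete the Von Frey clause from the basis of the sample size and power. State that Von Frey is a secondary measurement in volunteers with no claimed power.
2. In section 12, report the between-cream Von Frey difference with a 95% CI and the number tested in each arm.
3. Reconcile 7.2 with 8.2 so that the Von Frey group is the patients who had the baseline test planned in 8.2 before using the cream. Report by arm how many of them had no end-of-treatment test. This makes losses visible, including those due to the symptomatic condition in 7.2, but does not remove their effect.

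The cost is protocol wording and a count by arm, with no change to the planned 60 per arm. The sponsor gives up the powered claim for Von Frey.

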3. INTRODUCCIÓN

The impact of cancer in the western world and the growing number of people affected each year¹ means that new, increasingly effective and selective treatments are appearing relatively quickly. However, although these treatments are highly effective in killing tumour cells, they are not their only target. Molecules used in cancer treatments often affect healthy cells, causing side effects (nausea, diarrhoea, anaemia, immunosuppression, fatigue and hair loss). When antineoplastic therapies affect the sensory peripheral nervous system, they can cause peripheral polyneuropathy (NP or CIPN (Chemotherapy-Induced Peripheral Neuropathy)). The prevalence of this disease varies depending on the chemotherapy agent administered, affecting up to 80% of patients treated with taxanes (paclitaxel and/or docetaxel) or up to 95% of patients treated with oxyplatin². People with PN experience sensory discomfort, mainly in the extremities (numbness, dryness, tingling, burning, stinging, allodynia or hyperalgesia)³ which, over time, can

lead to the interruption of cancer treatment, with the risks that this entails. This condition often persists after the end of cancer treatment, which greatly affects the quality of life of those who suffer from it, as it can be uncomfortable when working, playing sports, carrying out household chores and even when socialising. In addition, the uncomfortable sensations can disturb sleep, which has an impact on mood. In general, people with NP caused by cancer treatments feel a great dissatisfaction with their skin.

Currently, there is no effective treatment for NP, and when the symptomatology is severe and limits patients' daily life, some doctors recommend taking antidepressants, such as duloxetine, or discontinuing chemotherapy treatment⁴. Although a number of clinical trials aimed at finding an effective treatment for NP have been conducted in recent years, none of them have proven to be effective. Therefore, understanding the mechanisms governing the development of PN and its treatment is a huge challenge in oncology as it is one of the main causes of chemotherapy withdrawal.

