The Institute for Research, Development and Innovation in Health Biotechnology of the Miguel [name] University of Elche (IDIBE-UMH) has been studying the mechanisms that govern skin imbalances for many years. This knowledge has been transferred to Prospera Biotech, and has been used to develop a line of creams for sensitive skin (trade name Nocisens). The mixture of fatty acids, tocopherol and innovative cosmetic ingredients means that Nocisens has a dual action on the stratum corneum. On the one hand, it strengthens the skin's barrier function by preventing water loss, which helps to increase hydration and re-establish the skin's protective function and, on the other hand, it prevents the accumulation of reactive oxygen species in the cells, protecting the skin from their harmful effects. These two actions help Nocisens cosmetic cream to create a feeling of well-being and comfort for the skin.

However, in cosmetics, the degree of acceptance of a product is a key element for adherence to treatment. We have therefore developed two formulations derived from Nocisens, PB-011 and PB-012, with slightly different texture, composition and properties in order to adapt them to the needs of the sensitive skin characteristic of palmo-plantar neuropathy mediated by chemotherapeutics.

Given that PN induced by treatments with chemotherapy or chemotherapeutic agents fused to monoclonal antibodies (immunocytostatic) is characterised by skin imbalances that affect the quality of life of the people who suffer from it, a parallel, randomised, double-blind, masked study is proposed in patients who are about to begin oncological treatment to compare the

degree of acceptance of PB-011 and PB-012 cosmetic creams in this population. The study involves two populations: (i) the population where PB-011 cream will be tested; and, (ii) the population that will test PB-012 cream. The duration of the project will be 12 months, and participants will have to apply the cream once a day on their hands during the period of chemotherapy treatment. A sample size of 60 volunteers per population has been estimated to ensure statistical significance. As a relevant variable for the patients, the degree of skin satisfaction will be assessed every fortnight by means of a questionnaire only in the case of discomfort in the hands and/or feet.

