6.1. Inclusion criteria

Patients must meet all the criteria that appear in this section to be included in the study.

- To be older than 18 years old.
- To be able to complete questionnaires.
- Give informed consent in writing.
- Being able to apply the product under test by oneself.
- To have been diagnosed with stage I-III primary cancer.
- To have received a maximum of one treatment session with chemotherapy (derivatives of taxane, platinum or vincristines).
- Eastern Cooperative Oncology Group (ECOG) performance status (PS) 0-2.
- Life expectancy greater than or equal to 6 months.

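### Section 6.3's 95% power presumes that essentially all 60 recipients per arm are analysed, but the plan conflicts on who is; for section 6's neuropathy subset it is about 94% or 90% at section 3's upper-limit incidences

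*Combined protocol and SAP*

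**What the plan says.** **Sample size (section 6.3).** The groups are defined by receipt of cream: "Two study populations are contemplated: (i) population that will receive the PB-011 cream; (ii) population that will receive the PB-012 cream". The size follows: "The number of volunteers for the study is 60 for each population". Its basis is a 2-point difference on a 0-10 satisfaction scale (or 2 points on the Von Frey scale), an SD of 3 in each group, significance at p<0.05, and "a probability of finding a statistically significant difference for the p-value <0.05 of 95"%. The section does not say whether the test is one- or two-sided. It makes no allowance for patients without neuropathy or without data.

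**Who is compared or measured.**

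- Section 6: once treatment is over, "the degree of cutaneous comfort will be compared between the patients who have developed peripheral neuropathy in both groups".
- Section 3: satisfaction is assessed fortnightly "by means of a questionnaire only in the case of discomfort in the hands and/or feet".
- Section 7.2: "Those subjects who develop skin sensitivity or peripheral neuropathy should undergo the following procedures". These include the end-of-treatment DLQI, cream-satisfaction and discomfort questionnaires. Section 8.2 likewise makes the end-of-treatment check-up conditional on sensory or skin discomfort.
- Section 12: the modified intention-to-treat set needs one use of the product and a satisfaction record. No symptom condition is stated.
- Annex IV: the first three items are unconditional. A second block is added for patients who had discomfort or neuropathy.

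**Incidence.** Section 3 describes neuropathy as "affecting up to 80% of patients treated with taxanes (paclitaxel and/or docetaxel) or up to 95% of patients treated with oxyplatin". Section 6.1 admits a wider range of regimens: "To have received a maximum of one treatment session with chemotherapy (derivatives of taxane, platinum or vincristines").

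**The concern.** Patients enter before neuropathy has appeared, so a comparison among those who develop it uses a subset whose size is unknown at enrolment. The stated 95% is tied to everyone who receives a cream. If fewer are analysed, the figure describes a comparison that will not be made.

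The study is meant to show which cream gives greater satisfaction (section 4), and the better-accepted one is to be marketed (section 2.3). A reader weighing a null result would rely on the stated 5% chance of missing a 2-point difference. As the plan stands, that reader cannot tell which patients the 5% refers to.

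**Working it through.** **Inputs.** Difference 2, SD 3, alpha 0.05, power 95% and 60 per arm (section 6.3). Upper-limit incidences 95% for oxaliplatin and 80% for taxanes (section 3). Standardised difference d = 2/3 = 0.667.

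**Step 1: reproduce the plan's figure.** For an unpaired comparison of two means, by the normal formula:

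n per arm = 2 × (1.960 + 1.645)² × 3² / 2² = 2 × 13.0 × 2.25 ≈ 58.5, so 59.

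The exact (noncentral) t calculation gives 59.45, so 60. A one-sided test would need only 49 (normal) or 50 (t), so two-sided 0.05 is inferred as the version that yields 60. Section 6.3's arithmetic is sound.

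**Step 2: the reserve.** At 60 per arm, power is 95.2% by the t calculation and 95.5% by the normal formula. At 59 it is 94.9% and 95.2%. The stated 95% therefore needs about 59 to 60 analysed per arm, depending on the formula. That leaves practically no room for non-cases or missing data.

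**Step 3: the section 6 set at section 3's upper limits, no data lost.** This assumes that the 2-point difference and SD 3 on the 0-10 satisfaction scale also hold among patients with neuropathy. Section 6.3 states them for all recipients.

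Normal power = Φ(d × √(n/2) − 1.960). For n = 57: 0.667 × √28.5 − 1.960 = 1.60, giving 94.5%. For n = 48: 0.667 × √24 − 1.960 = 1.31, giving 90.4%.

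| Analysed per arm | Source | Power, t | Power, normal |
|---|---|---|---|
| 60 | all recipients | 95.2% | 95.5% |
| 57 | 60 × 0.95 (oxaliplatin upper limit) | 94.2% | 94.5% |
| 48 | 60 × 0.80 (taxane upper limit) | 89.8% | 90.4% |

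On the t figures, the chance of missing a 2-point difference on that scale is 100 − 94.2 = 5.8% or 100 − 89.8 = 10.2%, against the stated 5%. Letting both the number of cases and the arm sizes vary under simple randomisation (section 5.2) gives average power of 94.0% and 89.4%.

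**Step 4: fewer analysed.** The documents give no incidence for other platinum agents, for vincristine regimens or for the wider symptomatic set, and no rate of data loss. Purely as illustrative assumptions, analysing 70%, 60% or 50% of each arm (42, 36 or 30 patients) gives t-based power of 85.5%, 79.7% or 71.9%.

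**The case against.** **The section 6 sentence may not define the analysis.** It stands under selection of subjects, while section 12 defines the analysed sets without mentioning neuropathy, and Annex IV's first items appear meant for everyone. This stands to the extent that the neuropathy subset cannot be treated as the settled analysed set. But section 12 requires a satisfaction record, and sections 7.2 and 8.2 schedule the end-of-treatment questionnaires for symptomatic patients, so it does not clearly bring the others back. The data notebook is a separate attachment and cannot settle this here.

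**The outcome differs.** Section 6 compares comfort, and section 8.1 measures satisfaction/comfort by DLQI. The 2 points and SD 3 belong to a 0-10 satisfaction scale or to Von Frey. This stands: the 94% and 90% describe an unpaired comparison on the 0-10 scale. They do not describe the DLQI main variable or the paired t test of section 12.

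**The loss is small and the study calls itself a pilot.** This also stands. It is about 1 point at 95% incidence and about 5 points at 80%.

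**Stronger readings the documents do not support.** A reader might infer that section 6.3 is miscalculated; it reproduces. A reader might infer that the 95% fails unless every one of the 60 is analysed; 59 gives 95.2% by the normal formula and 94.9% by the t calculation, and the plan does not name its formula. A reader might take 94% and 90% as ceilings for the whole trial. They rest on limits for oxaliplatin and taxanes only, and the wider symptomatic set could outnumber the neuropathy cases.

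**Conclusion.** The concern holds as a modest inconsistency about the analysed population. Section 6.3's 95% applies if about 59 to 60 per arm are analysed. Sections 3, 6, 7.2, 8.2 and 12 and Annex IV do not agree on who will be, and nothing is allowed for non-cases or lost data.

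If the section 6 set is used, power is about 94% (57 per arm) or about 90% (48 per arm), a shortfall of roughly 1 to 5 points. It falls further with lower incidence or lost data; sections 2.7 and 7.3 foresee withdrawals, including for lack of efficacy. These figures rest on three assumptions: a two-sided 0.05 unpaired test, the same difference and SD in the subset, and the 0-10 satisfaction scale as outcome. They do not show that the trial is badly underpowered or that it needs more patients. The point should be fixed, at the low end of that category.

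**What to change.** Name one analysed set and use it consistently in sections 6, 6.3, 7.2, 8.2 and 12 and in Annex IV. Keep 60 per arm and restate section 6.3 along these lines:

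*Power is about 95% (unpaired t test, two-sided 0.05, difference 2, SD 3, 0-10 satisfaction scale) if about 60 per arm are analysed, about 94% with 57 and about 90% with 48. Assumed incidence in the analysed set: __. Assumed loss of data: __. These figures do not apply to the DLQI main variable or to the paired t test in section 12.*

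The sponsor should confirm that the test is two-sided, since the plan does not say so.

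**Cost.** Mostly wording, and the stated power becomes slightly less favourable. If the named set goes beyond symptomatic patients, questionnaire collection in sections 7.2 and 8.2 must widen to match, with some extra follow-up work for the centres.
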